7.3. Subgroups

Where sample size allows ($n > 5$), the following endpoints will be analysed overall and separately for the subgroups stated below. The analyses will follow the methods described in [Section 10.1](#). More detail on the criteria for each subgroup can be found in [Section 9](#) where applicable.

Outcome	Supports Protocol Objective Number	Subgroups
CR, CRi and CR/CRi response rates by the end of InO treatment	Secondary Objective 2	Overall, and by number of salvage therapies in the pre-index observation period (0,1, ≥ 2).
Number and proportion of patients achieving MRD negativity	Secondary Objective 3	Overall, and by number of completed cycles of InO and by number of salvage therapies in the pre-index observation period (0,1, ≥ 2).
Number and proportion of patients surviving at 3,6 and 12 months after InO initiation	Secondary Objective 4	Overall, and separately in patients with and without follow-up HSCT and by number of salvage therapies in the pre-index observation period (0,1, ≥ 2).

Outcome	Supports Protocol Objective Number	Subgroups
Cause of death	Secondary Objective 4	Overall, and separately in patients with and without follow-up HSCT.
Median OS (95% CI)	Secondary Objective 4	Overall, and separately in patients with and without follow-up HSCT.
Proportion of patients who are relapse free at 3, 6 and 12 months after InO initiation	Secondary Objective 5	All patients, separately in patients with follow-up HSCT.
Median RFS (95% CI)	Secondary Objective 5	All patients, separately in patients with follow-up HSCT.
Proportion of patients initiated on each treatment	Secondary Objective 6	Per treatment (chemotherapy (blinatumomab, other). HSCT, CAR T-cell therapy).
Response to treatment	Secondary Objective 6	Overall, and per treatment (chemotherapy (blinatumomab, other). HSCT, CAR T-cell therapy).
Survival following treatment	Secondary Objective 6	Per treatment (chemotherapy (blinatumomab, other). HSCT, CAR T-cell therapy).
Number and proportion of patients experiencing VOD/SOS during the post-index observation period	Secondary Objective 7	All patients, and in the following subgroups: no HSCT prior to InO, at least 1 HSCT prior to InO, no post-InO HSCT and patients with at least 1 HSCT post-InO. Patients will be assigned to one of these 4 groups which will be analysed separately. For each group, grade of VOD/SOS and follow-up treatment (Follow-up chemotherapy after completion of chemotherapy and follow-up HSCT after HSCT) will be presented.

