Type of conditioning regimen for each HSCT	All patients	Primary objective	None	Frequency tables and percentages.	Excluded.
Proportion of patients treated with blinatumomab	All patients	Primary objective	None	Frequency tables and percentages.	Excluded.
Number of CAR T-Cell therapies	All patients	Primary objective	None	Frequency tables and percentages. Summary statistics.	Excluded.
Total duration of treatment with InO	All patients	Secondary Objective 1	None	Summary statistics.	Excluded.
Number of cycles of InO, per patient	All patients	Secondary Objective 1	None	Frequency tables and percentages. Summary statistics.	Excluded.
Interrupted cycles of InO	All patients	Secondary Objective 1	None	Frequency tables and percentages. Summary statistics.	Excluded.
Summary of reasons for interruption	All patients	Secondary Objective 1	None	Frequency tables and percentages.	Excluded.
Doses of InO prescribed	All patients	Secondary Objective 1	None	Frequency tables and percentages. Summary statistics.	Excluded.
Modification of doses of InO	All patients	Secondary Objective 1	None	Frequency tables and percentages. Summary statistics.	Excluded.
Summary of reasons for InO modifications	All patients	Secondary Objective 1	None	Frequency tables and percentages.	Excluded.
Proportion of patients treated with Azole antifungal therapy concomitant to InO treatment	All patients	Secondary Objective 1	None	Frequency tables and percentages.	Excluded.
CR, CRi and CR/CRi response rates by the end of InO treatment	All patients	Secondary objective 2	Overall, and by number of salvage therapies in the pre-index	The CR/CRi rate will be estimated as the number and proportion of patients who achieve CR/CRi divided by the total number	Standard imputation for dates (see Section 7). Otherwise excluded.

Outcome	Analysis Set	Supports Protocol Objective Number	Subgroups	Statistical Method	Missing Data
			observation period (0,1, ≥2)	of patients completing treatment with InO (defined as patients with a recorded date of discontinuation of InO). Patients who have not completed treatment with InO will not be included in CR/CRi rate. Kaplan-Meier analysis, time to best response (CR/CRi and CR/CRi) from the start of InO treatment to the end of InO treatment. The median with 95% CI will be calculated.	
Number and proportion of patients achieving MRD negativity	All patients	Secondary Objective 3	Overall, and by number of completed cycles of InO	Frequency tables and percentages. Summary statistics.	Excluded.

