Distribution of methods used to assess MRD negativity	All patients	Secondary Objective 3	None	Frequency tables and percentages.	Excluded.
Number and proportion of patients surviving at 3,6 and 12 months after InO initiation	All patients	Secondary Objective 4	Overall, and separately in patients with and without follow-up HSCT	Frequency tables and percentages.	Excluded.
Cause of death	All patients	Secondary Objective 4	Overall, and separately in patients with and without follow-up HSCT	Frequency tables and percentages.	Excluded.
Median OS (95% confidence interval)	All patients	Secondary Objective 4	Overall, and separately in patients with and without follow-up HSCT	Kaplan-Meier analysis, median OS measured as being from the date of InO initiation to the date of death. Patients alive at end of follow-up will be censored at date of last visit.	Standard imputation for dates (see Section 7). Otherwise excluded.
Proportion of patients who are relapse free at 3, 6 and 12 months after InO initiation	All patients	Secondary Objective 5	All patients, separately in patients with follow-up HSCT	Frequency tables and percentages.	Excluded.
Median RFS (95% CI)	All patients	Secondary Objective 5	All patients, separately in patients with	Kaplan-Meier analysis, from InO initiation to date of first relapse or date of	Standard imputation for dates (see Section 7).

PFIZER CONFIDENTIAL

Outcome	Analysis Set	Supports Protocol Objective Number	Subgroups	Statistical Method	Missing Data
			follow-up HSCT	last visit before data collection.	Otherwise excluded.
Median NRM (95% CI)	Patients undergoing follow-up HSCT	Secondary Objective 5	None	Kaplan-Meier analysis, from date of follow-up HSCT to date of death or the date of last visit before date of data collection. 95% CI will also be presented.	Standard imputation for dates (see Section 7). Otherwise excluded.
Proportion of patients initiated on each treatment	All patients	Secondary objective 6	Per treatment (chemotherapy (blinatumomab, other). HSCT, CAR T-cell therapy)	Frequency tables and percentages.	Excluded.
Response to treatment	All patients	Secondary objective 6	Per treatment (chemotherapy (blinatumomab, other). HSCT, CAR T-cell therapy)	Frequency tables and percentages.	Excluded.
Survival following treatment	All patients	Secondary objective 6	Per treatment (chemotherapy (blinatumomab, other). HSCT, CAR T-cell therapy)	Frequency tables and percentages.	Excluded.

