Number and proportion of patients experiencing VOD/SOS during the post-index observation period	All patients	Secondary objective 7	All patients, separately in patients with follow-up HSCT, by grade and follow-up treatment (Follow-up chemotherapy after completion of chemotherapy and follow-up HSCT after HSCT)	Frequency tables and percentages.	Excluded.
Treatments received for VOD/SOS	All patients	Secondary Objective 7	All patients, separately in patients with follow-up HSCT	Frequency tables and percentages.	Excluded.
Survival following treatment	All patients	Secondary Objective 7	All patients, separately in patients with follow-up HSCT	Frequency tables and percentages.	Excluded.
Number and proportion of patients experiencing grade 3 or 4 TRAEs	All patients	Secondary Objective 7	All patients, separately in patients with follow-up HSCT	Frequency tables and percentages.	Excluded.

Outcome	Analysis Set	Supports Protocol Objective Number	Subgroups	Statistical Method	Missing Data
Treatments received for grade 3 or 4 TRAE	All patients	Secondary Objective 7	All patients, separately in patients with follow-up HSCT	Frequency tables and percentages.	Excluded.
InO dose delay as a result of grade 3 or 4 TRAE	All patients	Secondary Objective 7	All patients, separately in patients with follow-up HSCT	Frequency tables and percentages.	Excluded.
Number and proportion of patients experiencing other liver dysfunctions	All patients	Secondary Objective 7	All patients, separately in patients with follow-up HSCT	Frequency tables and percentages.	Excluded.
Treatments received for other liver dysfunction	All patients	Secondary Objective 7	All patients, separately in patients with follow-up HSCT	Frequency tables and percentages.	Excluded.
InO dose delay as a result of other liver dysfunction	All patients	Secondary Objective 7	All patients, separately in patients with follow-up HSCT	Frequency tables and percentages.	Excluded.
Peripheral blood blast counts prior to follow-up HSCT	All patients	Secondary Objective 7	All patients, separately in patients with follow-up HSCT	Summary statistics.	Excluded.

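### SAP 7.3 asks for MRD and survival by prior salvage and VOD/SOS by prior HSCT; SAP 10.2.11 omits all three, and survival by salvage is planned without an estimate that handles censoring

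*SAP*

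**What the plan says.** SAP 7.3 is the dedicated subgroup section. It directs that the listed endpoints be analysed by the listed subgroups wherever a subgroup has more than 5 patients.

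- **MRD negativity:** "Overall, and by number of completed cycles of InO and by number of salvage therapies in the pre-index observation period" (0, 1, ≥2).
- **Survival at 3, 6 and 12 months:** "Overall, and separately in patients with and without follow-up HSCT and by number of salvage therapies in the pre-index observation period" (0, 1, ≥2).
- **VOD/SOS:** all patients, then four groups: "no HSCT prior to InO, at least 1 HSCT prior to InO, no post-InO HSCT and patients with at least 1 HSCT post-InO". Each patient is to be placed in one of the four.

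SAP 10.2.11 lists the same outcomes with shorter subgroup columns.

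- **MRD negativity:** "Overall, and by number of completed cycles of InO".
- **Survival at 3, 6 and 12 months:** "Overall, and separately in patients with and without follow-up HSCT". The method is frequency tables and percentages, and missing data are excluded.
- **VOD/SOS:** "All patients, separately in patients with follow-up HSCT, by grade and follow-up treatment".

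SAP 10.2.4 gives MRD overall and by cycles. SAP 10.2.5 treats survival at the three time points as a categorical variable. SAP 10.2.8 does not mention HSCT before InO. Median OS uses Kaplan-Meier ("Kaplan-Meier analysis, median OS measured as being from the date of InO initiation to the date of death"), and both tables split it only by follow-up HSCT. Under SAP 3.1.2, a living patient needs at least 3 months of follow-up to be included.

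**The concern.** There are two problems.

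First, an analyst working from 10.2.11 would not produce three breakdowns that 7.3 requires. With two lists and no rule of precedence, whether those breakdowns appear can be decided after the results are known. The lost splits are informative ones. Prior salvage and prior HSCT are fixed at the index date. Follow-up HSCT is not: when survival is timed from InO initiation, a patient must live long enough to be transplanted, which favours the HSCT group. If 10.2.11 is followed, that is the only split left on the 3/6/12-month survival row.

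Second, even if 7.3 is followed, survival by salvage is planned as a simple percentage. A patient alive but last seen at month 5 has no known status at month 6 or 12. The plan does not say whether such a patient counts as missing and is dropped, or counts as surviving. Dropping living patients while keeping early deaths pulls survival down; counting them all as alive pushes it up.

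**Working it through.** **Step 1. Compare the lists row by row.**

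| Outcome | SAP 7.3 | SAP 10.2.11 | Missing from 10.2.11 |
|---|---|---|---|
| CR/CRi rate | salvage | salvage | nothing |
| MRD negativity | cycles; salvage | cycles | salvage |
| Survival at 3/6/12 months | follow-up HSCT; salvage | follow-up HSCT | salvage |
| VOD/SOS | HSCT before InO; HSCT after InO; grade; follow-up treatment | follow-up HSCT; grade; follow-up treatment | HSCT before InO |
| Median OS | follow-up HSCT | follow-up HSCT | nothing |

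Three rows differ.

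**Step 2. Look for something that resolves the difference.** SAP 7.3 points to Section 9 for subgroup criteria, but Section 9 covers missing values. SAP 10.2.4 states expressly that its MRD denominator supersedes earlier ones; there is no such statement for subgroups. The n > 5 limit is not an explanation, because 10.2.11 leaves the splits out altogether while keeping salvage for CR/CRi.

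**Step 3. Check the 7.3 VOD/SOS groups.** Every patient has either no HSCT or at least one before InO, and either no HSCT or at least one after InO. Each patient therefore belongs to two of the four groups, and assignment to one of them is not possible as written. These are two binary factors.

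**Step 4. Effect of censoring on the survival percentages.** At 3 months there is none: every included patient has either died or has 3 months of follow-up. For later times, take an invented stratum of 8: deaths at months 1, 2, 7 and 9; two patients alive when last seen at months 4 and 5; two followed beyond month 12.

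| Handling of the two censored patients | 6 months | 12 months |
|---|---|---|
| Dropped | 4/6 = 67% | 2/6 = 33% |
| Counted as alive | 6/8 = 75% | 4/8 = 50% |
| Kaplan-Meier | (7/8)(6/7) = 75% | (7/8)(6/7)(3/4)(2/3) = 37.5% |

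**Step 5. Will the strata pass n > 5?** The SAP plans about 25 patients. The documents give no salvage distribution, so the shares below are assumptions. The chance that all three strata have at least 6 patients is the sum of N!/(a! b! c!) · p₁ᵃ p₂ᵇ p₃ᶜ over a, b, c ≥ 6 with a + b + c = N. For MRD the denominator in 10.2.4 is assessed patients in CR/CRi. Borrowing the 80.7% CR rate quoted in Protocol section 7 gives 25 × 0.807 ≈ 20 at most.

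| Assumed shares (0 / 1 / ≥2) | N = 25 | N = 20 (MRD) |
|---|---|---|
| equal thirds | 67% | 21% |
| 20 / 40 / 40 | 34% | 9% |
| 10 / 50 / 40 | 3% | under 1% |

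For the two prior-HSCT groups at N = 25, P(6 ≤ X ≤ 19) with X binomial is 38%, 81% and 97% if 20%, 30% or 40% had a prior HSCT (also assumed).

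**Step 6. Precision.** An observed 50% has an exact 95% CI of 12% to 88% at n = 6 and 16% to 84% at n = 8.

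**The case against.** The best reply is that 7.3 is directive and 10.2.11 is a summary that does not forbid the extra splits, so 7.3 governs and the summary was simply not updated. The protocol requires a salvage split only for CR/CRi, where the tables agree, and the study is descriptive with no hypothesis or decision rule. Much of this stands: aligning the lists is close to editorial. But the SAP does not say that 7.3 governs, and the analysis text in 10.2 sides with the shorter list.

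On censoring, 7.3 refers to the methods of 10.1, and 10.1.5 allows Kaplan-Meier where appropriate. The specific instructions in 10.2.5 and 10.2.11 nevertheless choose frequencies and percentages for this outcome. That choice also affects the overall row, but there Kaplan-Meier OS is planned alongside; for the salvage strata it is not. The amount of censoring is uncertain too. SAP section 7 ends the access window in February 2019, which leaves about 22 months to the 31 December 2020 cut-off, so only loss to follow-up would censor before month 12. SAP 3.1.2 runs the window to 31 December 2020, so patients starting in 2020 could be included with under 12 months of follow-up.

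Three stronger readings are tempting and are not supported:

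- **That the missing median OS by salvage is a contradiction.** Both tables omit it and the protocol does not ask for it.
- **That these are the only splits in the plan free of conditioning on a later event, or that no survival curve by a baseline factor is planned.** The exploratory endpoint and its analysis are blacked out, and the VOD/SOS risk-factor analysis within transplanted patients uses factors measured at HSCT.
- **That the dropped tables would certainly be reportable because 25/3 ≈ 8 exceeds 5.** That assumes equal strata, which the documents do not give.

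**Conclusion.** The point holds in two parts. Three outcome rows (MRD negativity, survival at 3/6/12 months, VOD/SOS) carry subgroup splits in 7.3 that are absent from 10.2.11 and from the corresponding analysis text, with no rule of precedence. Survival by salvage, as planned, also has no estimate that handles censoring at 6 and 12 months. The first part rests on the text alone and is minor to repair. The second is the more substantive. Its size depends on how many patients are alive with under 12 months of follow-up, which the documents do not state; the 33% to 50% range comes from an invented stratum and shows only what two censored patients in eight can do. No hypothesis test is affected. The change should be made, but the plan's main results do not depend on it.

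**What to change.** 1. In SAP 10.2.11, add number of prior salvage therapies (0, 1, ≥2) to the MRD and 3/6/12-month survival rows, and add prior HSCT (0 vs ≥1) to the VOD/SOS row. Carry the same splits into 10.2.4, 10.2.5 and 10.2.8.
2. In the 7.3 VOD/SOS row, replace assignment to one of four groups with two separate binary splits: HSCT before InO (0 vs ≥1) and HSCT after InO (0 vs ≥1).
3. In 10.2.5 and 10.2.11, report 3/6/12-month survival by salvage stratum as Kaplan-Meier estimates with 95% CI, with numbers at risk, for strata that pass n > 5.
4. State, before data are analysed, that this subgroup list is final.

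Median OS by salvage is optional; a sentence adding or declining it would be enough.

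The cost is SAP wording and a few extra tables from data already collected: prior salvage, prior HSCT, and dates of death or last visit. The downside is small strata with wide intervals, and some strata may fall below the n > 5 limit, most likely for MRD.

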Veno-occlusive disease (VOD; also known as sinusoidal obstruction syndrome [SOS]) was reported in INO-VATE ALL as a treatment related adverse event (TRAE) occurring on average 16 days after the last dose of InO, and especially in patients who proceeded onto hematopoietic stem cell transplant (HSCT) therapy after InO treatment^{6,7}. Occurrence of VOD/SOS was 13% in patients receiving InO versus <1% in patients receiving standard of care, and 22% versus 3%, respectively, in patients with follow-up HSCT⁷. Additional characteristics at initiation of treatment with InO and at follow-up HSCT were also tested by Kantarjian et al. that may help identify patients with follow-up HSCT most at risk of developing VOD/SOS⁷. Non-haematologic TRAEs were also observed which affected the lung, cardiac system and kidney^{6,8}.

InO was approved by the European Medicines Agency (EMA) in June 2017 for the treatment of adults with relapsed/refractory CD22-positive B-cell ALL and for adults with Philadelphia chromosome positive relapsed/refractory B-cell ALL who have failed previous treatment, to be marketed as BESPONSA®. BESPONSA® is administered in 3- to 4- week cycles at doses of 1.5 mg/m² to 1.8 mg/m² for a total duration of 2-3 cycles in patients proceeding to HSCT (third cycle added for patients not achieving CR/CRi and MRD negativity), and up to 6 cycles otherwise⁶.

InO recently gained recommendation from the National Institute for Health and Care Excellence (NICE) in the United Kingdom (UK) in line with the licensed indication on 9th August 2018⁹ (see **Annex 1**), and is now available in routine care practice throughout the UK. Prior to NICE approval, InO was made available to UK patients through a compassionate use program (CUP) run by Pfizer Inc. between June 2016 and October 2017 (see **Annex 1**), and via private purchase. As part of the CUP alone, approximately 75 patients were treated across 31 National Health Service (NHS) Trusts, each Trust treating between 1 and 15 patients. Patient level data is available in medical records, enabling a retrospective chart review to be conducted.

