9.5. Study size

This is a descriptive study and there is no *a priori* hypothesis specified, therefore a formal power calculation is not required. The sample size of approximately 25 patients has been based on the number of patients expected to be available at three centres that individually treated the largest number of patients with InO.

For the assessment of risk factors for VOD/SOS in patients with follow-up HSCT, the following rationale applies regarding sample size. Usually, 10 events per variable are required to be able to fit a Cox proportional hazard model with sufficient accuracy¹¹. The Kantarjian analysis identified 4 risk factors in a univariate analysis and 2 risk factors in the

multivariate analysis (See section 7.3). In addition, 47% of patients (77 out of 164 patients) had follow-up HSCT and VOD/SOS occurred in 22% of patients with follow-up HSCT in the INO-VATE ALL trial⁷. Therefore, it derives that for the univariate analysis (i.e., a model which fits one variable at a time), 45 patients with follow-up HSCT and 96 patients overall would be needed to be enrolled into the study. For the multivariate analysis fitted with the 2 significant risk factors previously identified, 90 patients with HSCT and 192 patients overall would be need to be enrolled. Therefore, considering the sample size of the study, if risk factors cannot be estimated using a multivariate model, all factors will be assessed using a univariate model, if possible.

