3.1.3. Data Source

Data for this study will be initially collected through retrospective data collection from three to five NHS Trust cancer services in the UK which were part of the CUP (additional centres may be added at a later stage if the target sample size is not achieved). The sample size of approximately 25 patients has been based on the number of patients expected to be available at three centres that individually treated the largest number of patients with InO. Further detail regarding sample size can be found in section 9.5 of the study protocol.

Data on patient demographic and clinical characteristics, treatment patterns, outcomes, and AEs will be collected from paper based and/or electronic hospital medical records (as applicable at each site) by members of the patient's direct care team in anonymised-coded form.

Data will be collected using anonymized-coded eCRFs designed specifically for the study. Participants will be identified in all study records by a unique participant identification number to allow data management queries to be resolved with reference to source medical records while preserving patient confidentiality.

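### SAP 7.3 tells the analyst to put each patient in one of four VOD/SOS groups, but the groups are two overlapping yes/no splits and every patient belongs to two of them

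*SAP*

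**What the plan says.** SAP section 7.3 (Subgroups), in the row for patients with VOD/SOS during the post-index period, asks for a result in all patients and in these groups: "no HSCT prior to InO, at least 1 HSCT prior to InO, no post-InO HSCT and patients with at least 1 HSCT post-InO". The next sentence reads: "Patients will be assigned to one of these 4 groups which will be analysed separately". Section 7.3 limits subgroup analyses to groups of more than 5 patients and refers to section 9 for the criteria that define each subgroup. Section 9 deals only with missing values and contains no such criteria.

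The SAP describes the same outcome differently in three other places:

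- Section 8, secondary objective 7: all patients, and patients with and without follow-up HSCT.
- Section 10.2.8: overall, by grade, by follow-up chemotherapy and by follow-up HSCT, if sample size allows.
- Section 10.2.11: "All patients, separately in patients with follow-up HSCT, by grade and follow-up treatment".

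None of the three mentions the prior-HSCT groups or the one-of-four rule.

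**The concern.** The first two groups divide the whole cohort by transplant before InO. The last two divide the same cohort by transplant after InO. A patient with one transplant before InO and none after it meets the second definition and the third, and the same holds for every other history: each patient meets exactly two. A rule that places each patient in only one group must remove that patient, and any VOD/SOS event the patient had, from another group where they belong.

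The SAP does not say which membership takes priority. Two analysts could each follow section 7.3 and report different subgroup proportions from identical data. VOD/SOS is a named event in the safety objective, and section 7.3 is the only place where the SAP defines prior-HSCT groups for it. For that split there is no alternative text to fall back on.

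**Working it through.** **Logic, with no assumptions.** Let the cohort have N patients. Full membership gives (no prior) + (prior) = N and (no post) + (post) = N, so the four denominators sum to 2N. Single assignment makes them sum to N. If all four combinations of prior and post-InO HSCT occur, each group of one pair overlaps each group of the other. At most two groups can then be complete; they must form one pair, and the other pair is empty.

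**Inputs from the documents.**
- N: "The sample size of approximately 25 patients has been based on the number of patients expected to be available at three centres" (SAP 3.1.3).
- Follow-up HSCT share: "47% of patients (77 out of 164 patients) had follow-up HSCT" (Protocol 9.5). Check: 77/164 = 0.4695.
- VOD/SOS with follow-up HSCT: "VOD/SOS occurred in 22% of patients with follow-up HSCT" (Protocol 9.5).
- VOD/SOS overall: "Occurrence of VOD/SOS was 13% in patients receiving InO" (Protocol section 7).

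**Input assumed.** The documents give no prior-HSCT share. I take 20%, independent of follow-up HSCT and of VOD/SOS, and vary it below.

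**The plan's own figures.** The documents state no sizes for the four groups. The only VOD/SOS size calculation, in Protocol 9.5, reproduces to within a patient: 10/0.22 = 45.5 (stated 45) and 45/0.47 = 95.7 (stated 96); 20/0.22 = 90.9 (stated 90) and 90/0.47 = 191.5 (stated 192). It concerns the risk-factor model and does not bear on this point.

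**Full membership, N = 25.**
- Post-InO HSCT: 25 × 0.4695 = 11.7. No post-InO HSCT: 25 − 11.7 = 13.3.
- Prior HSCT: 25 × 0.20 = 5.0. No prior HSCT: 20.0.
- Implied VOD/SOS without follow-up HSCT: (0.13 − 0.4695 × 0.22) / 0.5305 = 0.050, about 5%.
- Expected events: 25 × 0.13 = 3.25, of which 11.7 × 0.22 = 2.6 are in the follow-up-HSCT group.

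**Single assignment under three allocation orders** (expected patients, expected VOD/SOS):

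| Group | Full membership | Post-InO HSCT first, rest by prior status | Prior status first | At least 1 prior first, rest by post status |
|---|---|---|---|---|
| No prior | 20.0, 13% | 10.6, 5% | 20.0, 13% | empty |
| Prior | 5.0, 13% | 2.7, 5% | 5.0, 13% | 5.0, 13% |
| No post | 13.3, 5% | empty | empty | 10.6, 5% |
| Post | 11.7, 22% | 11.7, 22% | empty | 9.4, 22% |
| Sum of patients | 50 | 25 | 25 | 25 |

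In the second column, 20.0 × 0.5305 = 10.6 and 5.0 × 0.5305 = 2.7. The patients who remain are those without follow-up HSCT, so the prior-HSCT groups take on the 5% rate of that stratum. In the last column, 20.0 × 0.4695 = 9.4.

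**Sensitivity.** With post-InO HSCT assigned first, the no-prior group falls from 22.5 to 11.9 patients at a 10% prior share, from 17.5 to 9.3 at 30%, and from 12.5 to 6.6 at 50%. The fall from 13% to about 5% is the same at every share and does not depend on N. At a 30% share the prior group has 7.5 expected patients under full membership and 4.0 under this order, so the rule alone would take it below the SAP's threshold of more than 5.

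**The case against.** A reader might infer that the VOD/SOS proportion after follow-up HSCT will be wrong and cannot be set against the 22% the protocol cites. The documents do not support that. SAP sections 8 and 10.2.11 plan a follow-up-HSCT result without the one-of-four rule, and the all-patients proportion never passes through it. Where an allocation order only shrinks the follow-up-HSCT group (11.7 to 9.4 above), the expected proportion stays at 22% under the stated independence; what is lost is precision. With post-InO HSCT assigned first, that group is complete.

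The rule also cannot be applied silently. With no allocation order given, a programmer would have to ask, and either likely answer (two separate splits, or the four cells of prior by post-InO HSCT) gives valid proportions. This is a fair account of what would probably happen. But the four cells are not the groups listed, and at a 20% prior share the two cells with prior HSCT would have 2.7 and 2.3 expected patients, too few under the SAP's own threshold. Adopting two splits means departing from the written rule.

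Finally, the stakes are modest. The study is descriptive, VOD/SOS is one of several events in a secondary objective, and the significant risk factors listed in Protocol 9.3 do not include prior HSCT. All of this stands and limits the importance of the point. It does not make the rule workable.

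**Conclusion.** The assignment rule in SAP 7.3 contradicts the groups it refers to. That conclusion follows from the definitions alone. Half of all group memberships are lost (25 of 50 at N = 25), and which groups suffer depends on an order the SAP does not state. One order moves the expected VOD/SOS proportion in the prior-HSCT groups from 13% to about 5% and empties the no-post group; another leaves the prior-HSCT groups correct and empties both post-InO groups. These sizes are illustrative: they carry over the INO-VATE rates quoted in the protocol and assume a prior-HSCT share and independence that the documents do not give.

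The main damage is to the prior-HSCT groups, which only section 7.3 defines for this outcome, and to agreement between sections 7.3, 8, 10.2.8 and 10.2.11. It should be corrected before analysis, but it does not threaten the overall VOD/SOS result or the comparison after follow-up HSCT.

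**What to change.** Replace the assignment sentence in SAP 7.3 with: *VOD/SOS will be tabulated (a) by HSCT before InO (0 vs ≥1) and (b) by HSCT after InO (0 vs ≥1); each patient contributes once to each classification.* Each classification then sums to N.

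Use the same subgroup list in section 8 (secondary objective 7), section 10.2.8 and section 10.2.11. Correct or remove the reference in 7.3 to section 9 for subgroup criteria. A two-by-two table of counts (prior by post-InO HSCT) could be added but is optional.

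The cost is SAP wording and the matching table shell. Protocol Annex 2 already collects the number of prior transplants and each transplant after InO initiation, so no new data are needed.
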